9.7.3. Partial Response

Partial response will be defined as >30% decrease in the sum of the largest diameter of all targeted tumors.

9.7.4. Stable Disease

Stable disease will be defined as <30% decrease in the sum of the largest diameter of all targeted tumors.

9.7.5. Local Failure

Local failure will be defined as >20% increase in the sum of the largest diameter of all targeted tumors.

9.7.6. Distant Failure

Distant failure (e.g. metastatic disease) will be defined as the appearance of distant cancer deposits consistent with metastatic spread of cancer outside the intended treatment area.

10. ENGINEERING, MANUFACTURING, HANDLING AND ACCOUNTABILITY OF INVESTIGATIONAL DEVICE

10.1. Manufacturing, Packaging and Labeling

The Galil Medical Cryoablation System and needles are manufactured, packaged and labeled according to current Good Manufacturing Practices (cGMP) and applicable international, national and local regulations, laws, and guidelines.

10.2. Handling and Storage

The Galil Medical Cryoablation System, needles, necessary equipment, and disposables are handled and stored according to Galil Medical's specifications.

CUC10-LNG06-04 Page 18 of 38

10.3. Recall of Investigational Device

The Galil Medical Cryoablation System and needles are designed and built in accordance to IEC 60601-1 standard performance and safety specifications for surgical medical instruments. Any recall of the investigational device will be done in accordance with applicable international, national and local legislation and guidelines, as well as the sponsor's requirements.

11. STATISTICAL ANALYSIS

11.1. General Methods

This is a prospective single-arm feasibility study designed to determine the safety of Galil Medical's Cryoablation System and needles in cryoablation of lung tumors, as well as give an insight into the efficacy of the treatment. This study is not powered for formal statistical analysis. All comparisons will be qualitative in nature. Descriptive results of this feasibility study may be used to generate hypotheses for a pivotal study.

11.2. Sample Size

Because estimates from this study will be used to power the pivotal study, this study must be able to provide such estimates. A sample size of at least 30 patients, but up to 40 patients, is considered clinically sufficient to give indications of both safety and potential efficacy. With this sample size, we feel we can decide whether to proceed to a pivotal study, determine endpoints for such a study, and design the study to answer the proposed hypotheses. Up to approximately 10 additional patients may be enrolled to account for patients who do not meet inclusion/exclusion criteria involving non-standard clinical practices.

11.3. Missing Data

Missing data will be prospectively minimized through training of the participating investigator and site staff, and through appropriate clinical trial management. Every effort will be made to collect all data points in the study. All patient data that is available on patients who drop out during the course of the study will be included where possible.

11.4. Analysis Populations

All analyses will be performed on all subjects with a Galil Medical Cryoablation System and needles as the attempted treatment. A per-protocol analysis may also be done, removing subjects who did not have a complete treatment and those that did not meet the study criteria but were enrolled.

11.5. Analysis

11.5.1. General Analysis

Data will be analyzed using descriptive statistics. Continuous variables (e.g., age) will be summarized by the number of patients, mean, standard deviation, median, interquartile range, minimum and maximum. Categorical variables (e.g., race) will be summarized by frequencies and percentages of patients in each category.

11.5.2. Efficacy Endpoints

The efficacy endpoint for this study is defined as follows: local tumor control in patients with pulmonary metastatic disease at 3, 6, 12, 24, 36, 48 and 60 months post cryoablation.

Tumor control will be determined by examining the change from baseline at follow-up visits. Post-treatment imaging including CT/MRI will be reported for baseline and follow-up visits. Tumor control will be defined by the criteria defined in Section 9.7 of this protocol.

CUC10-LNG06-04 Page 19 of 38

Patients are allowed up to 5 tumors so tumor control will be calculated on a per tumor level as well as a patient level. To be considered a success on a patient level all tumors treated during the baseline procedure must meet the tumor control criteria at that follow-up visit.

The local tumor control counts and rates will be presented along with the 95% two-sided confidence intervals for the rates. The rate at the each visit will be defined as the proportion of tumors/patients experiencing tumor control at a specific timepoint out of the number of patients who complete a follow-up visit at that timepoint.

11.5.3. Safety Endpoints

The safety endpoint for this study is to assess the incidence and severity of intra-operative events, post operative adverse events, serious adverse events and unanticipated adverse device effects related to the cryoablation procedure.

Point estimates and two-sided 95% confidence intervals will be generated for cryoablation related adverse events.

11.5.4. Other Endpoints

Technically successful treatment definition

A technically successful treatment will be defined by an ablation volume encompassing the tumor with at least a 5 mm margin.

Technical success will be calculated on a per tumor level as well as a patient level. To be considered a technical success on a patient level all tumors treated during the baseline procedure must meet the technical success criteria.

Disease recurrence or progression definitions

Disease recurrence or progression will be determined locally by evidence of an increase in tumor size and/or contrast enhancement.

Disease-specific survival rate is defined as the time in days from cryoablation procedure to death due to lung cancer. Patients who are alive will be censored at the date of their last visit. Patients who have died from causes other than lung cancer will be censored at the time of death. Disease-specific survival rates will be summarized by using Kaplan-Meier methodology.

Overall survival rate is defined as the time in days from cryoablation procedure to death. Patients who are alive will be censored at the date of the last visit. Overall survival rates will be summarized by using Kaplan-Meier methodology.

Time to recurrence is defined as the time in days from cryoablation procedure to disease recurrence or progression. Patients without disease recurrence or progression will be censored at the date of their last visit or their date of death (due to any cause). Recurrence free survival rates will be summarized by using Kaplan-Meier methodology.

Intra-procedural data

Initial cryoablation procedure information including the type of procedure, tumor size and number, cryoablation needle type and the number of each type of needle used, freeze and thaw times, method of thaw (active or passive), and ice formation and how it encompasses the tumor will be summarized.

Physical performance and quality of life

Physical performance (ECOG and KPS) and quality of life (SF-12) assessments will be made by examining the change in the baseline scores to those reported post-operatively as defined in Sections 9.3.1 and 9.5, respectively.

CUC10-LNG06-04 Page 20 of 38

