5.3. Other Endpoints

Other endpoints for this study include, but are not limited to:

- Assessing overall disease specific survival at 3, 6, 12, 24, 36, 48 and 60 months post cryoablation.
- Assessing time to disease recurrence or progression.
- Assessing the changes in physical function and quality of life over time. (See Section 11.5.4)
- Assessing cryoablation technical success. (See Section 11.5.4)

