#### **Analysis Methods**

Patients may have up to five tumors so tumor control will be calculated on a per tumor level as well as a patient level. To be considered a success on a patient level all tumors treated during the baseline procedure must meet the tumor control criteria at that follow-up visit.

Post-treatment imaging including CT/MRI will be reported for baseline and follow-up visits. Tumor control for each time point will be determined by examining the change from baseline, and will be defined as:

Complete Response – Tumor disappearance or a  $\geq$  75% decrease in the greatest transaxial diameter ( <25% of original size).

Partial Response – A <75% but ≥30% decrease in the greatest trans-axial diameter.

**Stable Disease** – No change, allowing for a <30% decrease up to a <20% increase in the greatest trans-axial diameter.

**Local Failure** – A ≥20% increase in the greatest trans-axial diameter.

**Local Control** – Local control will be defined as the absence of local failure. Tumors in complete response, partial response and stable disease will all be in local control.

**Distant Failure** – Distant failure (e.g. metastatic disease) will be defined as the appearance of distant cancer deposits consistent with metastatic spread of cancer outside the intended treatment area.

The local tumor control counts and rates will be presented along with the 95% two-sided confidence intervals for the rates. The rate at the each visit will be defined as the proportion of tumors/patients experiencing tumor control at a specific time point out of the number of patients who complete a follow-up visit at that time point.

Efficacy analyses will be performed on the ITT population. Analysis of the PP population may be done in support of the ITT analysis. No formal statistical hypothesis testing will be performed for efficacy endpoints.

Confidential Page 3 of 9

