#### Disease recurrence or progression

Disease specific survival, overall survival, and time to disease recurrence or progression will be analyzed by Kaplan-Meier methodology. These measures are defined as:

**Disease-specific survival** will be analyzed as the time in days from cryoablation procedure to death due to lung cancer. Patients who are alive will be censored at the date of their last visit. Patients who have died from causes other than lung cancer will be censored at the time of death.

**Overall survival** will be analyzed as the time in days from cryoablation procedure to death. Patients who are alive will be censored at the date of the last visit.

Freedom from disease recurrence or progression will be analyzed as the time in days from cryoablation procedure to disease recurrence or progression, determined locally by evidence of an increase in tumor size and/or contrast enhancement. Patients without disease recurrence or progression will be censored at the date of their last visit or their date of death (due to any cause).

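### The disease recurrence or progression event lists no new lesions and has no size threshold, so the curve does not match its name and contradicts the efficacy endpoint

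*Protocol*

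**What the plan says.** - **Endpoint.** Protocol 5.3 lists, among the other endpoints, "Assessing time to disease recurrence or progression".
- **Event.** Protocol 11.5.4: "Disease recurrence or progression will be determined locally by evidence of an increase in tumor size and/or contrast enhancement". The SAP (Supportive Endpoint Analyses, Disease recurrence or progression) uses the same two triggers: "determined locally by evidence of an increase in tumor size and/or contrast enhancement".
- **Censoring.** Protocol 11.5.4: "Patients without disease recurrence or progression will be censored at the date of their last visit or their date of death", whatever the cause of death. The SAP does the same. The Protocol labels the Kaplan-Meier result recurrence-free survival; the SAP labels it freedom from recurrence or progression.
- **Distant Failure.** Protocol 9.7.6 defines it as the "appearance of distant cancer deposits consistent with metastatic spread of cancer outside the intended treatment area". The SAP, under the efficacy Analysis Methods, carries the same definition: "Distant failure (e.g. metastatic disease) will be defined as the appearance of distant cancer deposits". Neither document links it to a time-to-event endpoint.
- **Size rule in the efficacy endpoint.** The SAP defines Stable Disease as "No change, allowing for a <30% decrease up to a <20% increase in the greatest trans-axial diameter". Growth of 20% or more is Local Failure, and everything short of that is Local Control. Protocol 9.7.1 also defines local control as absence of local failure, and 9.7.5 sets local failure at growth above 20% in the summed largest diameters.
- **New disease elsewhere in the plan.** The SAP's Additional Data Summaries tabulate new tumors at follow-up and further metastatic disease, descriptively only.

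**The concern.** All patients enter with Stage 4 disease (Protocol 7.2.3), where spread to new sites is an expected form of progression. An endpoint named for disease progression should register it. As written, the event responds only to growth or enhancement, and the category that both documents created for new disease is not used.

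The same rule is looser than the efficacy endpoint at the treated site. Any increase counts, and so does enhancement alone, which appears in no response category. The two results can therefore disagree about the same tumor on the same scan.

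At stake is how the curve is read. It is neither time to disease progression, because new disease is not listed, nor time to local failure, because its threshold is not the one used for local failure. Protocol 11.2 says that estimates from this study will be used to power a pivotal study and determine its endpoints. It does not name this curve as one of those estimates.

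**Working it through.** The plan gives no event rate, power or precision figure for this endpoint, so there is nothing to reproduce. The main check is to put the two rules side by side.

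**1. Same scan, two rules (growth taken from baseline)**

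| Finding at follow-up | Progression rule (Protocol 11.5.4, SAP) | Efficacy categories (SAP) |
|---|---|---|
| New metastases, treated sites quiet | No listed trigger; censored | Distant Failure; treated tumors in Local Control |
| Treated tumor +10% | Event | Stable Disease, Local Control |
| Enhancement, diameter unchanged | Event | Stable Disease, Local Control |
| Treated tumor +25% | Event | Local Failure |

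Only the last row agrees. For the largest eligible tumor, 3.5 cm (Protocol 7.2.5), the 20% limit is 3.5 × 1.20 = 4.2 cm. Every diameter above 3.5 cm and below 4.2 cm is progression in one analysis and Local Control in the other.

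**2. Effect of omitting new lesions, taken alone (illustration)**

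Inputs: proportion with a local event L = 20% (7/35 tumors) or 35% (7/20 patients), borrowed from the series of 35 metastatic tumors in 20 patients summarized in Protocol 3.2; proportion with a distant event D = 10% to 60%, assumed because the documents give none; N = 30 or 40. Local and distant events are assumed independent, at one fixed time.

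Freedom from event as written = 1 − L. With new lesions counted = (1 − L)(1 − D). Extra events = N(1 − L)D.

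| L | D | As written | New lesions counted | Difference (points) | Extra events, N = 30 | Extra events, N = 40 |
|---|---|---|---|---|---|---|
| 20% | 10% | 80% | 72% | 8 | 2.4 | 3.2 |
| 20% | 20% | 80% | 64% | 16 | 4.8 | 6.4 |
| 20% | 40% | 80% | 48% | 32 | 9.6 | 12.8 |
| 20% | 60% | 80% | 32% | 48 | 14.4 | 19.2 |
| 35% | 10% | 65% | 58.5% | 6.5 | 2.0 | 2.6 |
| 35% | 20% | 65% | 52% | 13 | 3.9 | 5.2 |
| 35% | 40% | 65% | 39% | 26 | 7.8 | 10.4 |
| 35% | 60% | 65% | 26% | 39 | 11.7 | 15.6 |

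This holds L fixed, so it shows one of the two effects only.

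**3. The threshold works the other way**

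Let f be the share of events as written that would still qualify under the efficacy endpoint's rule. Freedom from event after both corrections = (1 − fL)(1 − D). It equals 1 − L when f = [1 − (1 − L)/(1 − D)]/L.

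- L = 35%, D = 10%: 0.65/0.90 = 0.722; f = 0.278/0.35 = 0.79.
- L = 35%, D = 20%: 0.65/0.80 = 0.8125; f = 0.1875/0.35 = 0.54.
- L = 20%, D = 10%: 0.80/0.90 = 0.889; f = 0.111/0.20 = 0.56.

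If f is below these values, the corrected curve lies above the one now planned. If D is at least as large as L, it cannot, because (1 − fL)(1 − D) ≤ 1 − D ≤ 1 − L. The documents give neither D nor f, so the sign of the net change cannot be determined.

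**The case against.** The strongest defense is that a local endpoint was intended. The study objective (Protocol 4.1) is local tumor control, and the word locally in the event rule may mean at the treated site. The endpoint would then be sound in kind and wrong in name, and renaming it would be enough on that score. This stands as an alternative fix. It does not cure the threshold conflict, which is a conflict between two local rules.

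The word may instead mean as judged by the site. Protocol 8.5 and 8.6 schedule a general assessment of disease progression at the imaging visits, and a site could record a new enhancing lesion as contrast enhancement. A reader might therefore infer too much in saying that new metastases can never count, or that the rule is confined to existing tumors: the text says neither. What it supports is that new lesions are not listed. Counting them would then rest on each site's interpretation.

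The stakes are also limited. This is an other endpoint in a study that Protocol 11.1 describes as not powered for formal analysis. New tumors, further metastatic disease and new treatments are tabulated, and overall survival is analyzed, so the information is not lost. All of that stands and limits the severity, but it does not make the curve match its label.

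**Conclusion.** The point holds. The event definition omits new lesions although Distant Failure is defined in both documents, and it has no size threshold, so it contradicts the efficacy endpoint on the same scan. This follows from the text and needs no numerical assumption.

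Its size cannot be estimated from the documents. The 6.5 to 48 percentage points in the illustration cover only the omission of new lesions, and rest on borrowed local rates, assumed distant rates and independence.

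Two stronger conclusions are tempting and unsupported:

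- A reader might infer that the curve overstates freedom from progression overall. The omission does push that way, but counting any growth or enhancement pushes the other way, and the net direction is unknown.
- A reader might subtract 7 local from 19 overall recurrences in the cited series (0.543 × 35 = 19) and infer that 12 of 19, or 63%, of recurrences would be missed. Protocol 3.2 places the 7 local recurrences in a 9-12 month period, while the 54.3% is an overall figure with median follow-up of 21 months. The denominator of 35 for the 54.3% is itself inferred. The counts are per tumor, whereas this endpoint is timed per patient. The difference need not be distant recurrence.

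The efficacy endpoint and the sample size are unaffected. The definition should be corrected before the curve is reported under its present name.

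**What to change.** Amend Protocol 11.5.4 and the SAP together. Define the disease event as the earlier of:

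- Local Failure, with the same threshold and the same handling of enhancement as the efficacy endpoint. Enhancement should be in both definitions or in neither. Name one threshold, since Protocol 9.7.5 and the SAP word it differently.
- Distant Failure as in Protocol 9.7.6, dated at the scan that shows it.

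Report time to local failure as a separate curve.

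If a local-only endpoint was intended, rename it time to local failure, align its threshold and enhancement rule with the efficacy endpoint in the same way, and report distant failure separately.

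The cost is wording, one extra Kaplan-Meier curve and two checks. CT/MRI and a progression assessment are already scheduled from Month 3 (Protocol 8.5, 8.6). However, the SAP lists new disease without saying that onset dates are captured, so the case report form needs checking. Screening imaging covers lungs, liver and adrenal glands (Protocol 8.1), while the follow-up sections and 9.6 state no anatomical coverage. Consistent coverage should be confirmed before distant failure is used as an event; it should not be assumed that no further data are needed.

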7.2. Inclusion Criteria

Eligible patients for this study must meet all of the following criteria:

- 7.2.1. Patient must be at least 18 years old.
- 7.2.2. Patient has signed a written informed consent.
- 7.2.3. Patient presents with Stage 4 pulmonary metastatic disease with metastatic disease previously confirmed by prior biopsy; or
 Patient presents with Stage 4 pulmonary metastatic disease previously confirmed on
 - Patient presents with Stage 4 pulmonary metastatic disease previously confirmed on imaging (e.g. CT or MRI) with known (biopsied) primary disease.
- 7.2.4. Patient has up to 3 local metastases unilaterally targeted by cryoablation. (treatment in both lungs must be on separate treatment days) Maximum number of pulmonary tumors bilaterally per patient will be 5 total pulmonary tumors.
- 7.2.5. Targeted tumor(s) defined as intra pulmonary or pleural with a maximum size of 3.5 cm.
- 7.2.6. The target tumor is determined (by CT/MRI images) to be in a location where cryoablation is technically achievable based on the proximity of adjacent organs and structures.
- 7.2.7. ECOG performance status of 0-2.
- 7.2.8. Karnofsky Performance Scale (KPS) score ≥60.
- 7.2.9. Platelet count >50,000/mm³ within 60 days prior to study treatment.
- 7.2.10. INR < 1.5 within 60 days prior to study treatment.
- 7.2.11. Patient has a life expectancy of >3 months.
- 7.2.12. Patient is clinically suitable for cryoablation procedure.

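### Protocol 11.5.4 gives the name recurrence-free survival to a Kaplan-Meier curve that censors deaths; the SAP corrects the name but keeps a curve whose complement is not the risk of recurrence

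*Protocol*

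**What the plan says.** Protocol 5.3 lists time to recurrence or progression among the other endpoints. Protocol 11.5.4 defines it: "Time to recurrence is defined as the time in days from cryoablation procedure to disease recurrence or progression". Patients without that event are "censored at the date of their last visit or their date of death (due to any cause"). The same paragraph then names the output: "Recurrence free survival rates will be summarized by using Kaplan-Meier methodology".

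The SAP, section Disease recurrence or progression, changes the name and nothing else: "Freedom from disease recurrence or progression will be analyzed as the time in days from cryoablation procedure to disease recurrence or progression". Its censoring rule is the same: "Patients without disease recurrence or progression will be censored at the date of their last visit or their date of death". So is its estimator: "time to disease recurrence or progression will be analyzed by Kaplan-Meier methodology".

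The measure therefore has three names across Protocol 5.3, Protocol 11.5.4 and the SAP, with one event, one censoring rule and one estimator. Neither document defines a composite of recurrence or death, and neither names a competing-risk estimator. Overall survival is analysed separately in both.

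**The concern.** Recurrence-free survival is the probability of being alive without recurrence, so a death ends it. Under the protocol's rule no death ever lowers the curve, so the rule does not produce the quantity it names.

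The SAP's name matches its event, but one difficulty remains. A Kaplan-Meier curve that censors deaths treats a patient who has died as someone who could still recur later. One minus that curve is then not the proportion of treated patients who recur.

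Death before recorded recurrence is plausible here. Patients have Stage 4 disease, the survival requirement at entry is only "Patient has a life expectancy of >3 months" (Protocol 7.2), and follow-up runs to 60 months (Protocol section 5). After month 12 scheduled imaging is yearly (Protocol Table 1 and 8.6), so a patient can progress and die between scans and be censored as recurrence-free.

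What is at stake is how the curve is read. Taken as recurrence-free survival, it looks too favourable. Taken through its complement as recurrence risk, it looks too unfavourable.

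**Working it through.** The plan gives no expected recurrence rate, event count or precision for this endpoint, so there is no figure of its own to reproduce. The check covers direction first, then size under stated assumptions.

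**Direction.** At each event time let n be the number at risk, r the recurrences and d the deaths without recurrence.

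- Planned curve: K = product of (1 − r/n).
- Recurrence-free survival: S = the same product with an extra factor (1 − d/n) at each death. Every extra factor is at most 1, so S ≤ K.
- Complement of the planned curve: 1 − K = sum of K(just before) × r/n.
- Cumulative incidence (Aalen-Johansen): F = sum of S(just before) × r/n. Since S ≤ K, F ≤ 1 − K.

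Both overstatements therefore hold together. K exceeds S as soon as anyone dies without recurrence. 1 − K exceeds F when such a death comes before a later recurrence.

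**Hand example.** Of 40 patients, 10 die without recurrence at month 6, 10 recur at month 12 and 20 stay event-free.

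- Planned curve: 1 − 10/30 = 66.7%. Recurrence-free survival: (30/40) × (20/30) = 50.0%.
- Complement: 33.3%. Proportion who recurred: 10/40 = 25.0%.

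**Size.** Assume constant cause-specific hazards, each obtained from an annual percentage p as −ln(1 − p): a for recurrence, b for death without recurrence. Then:

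- K = exp(−at)
- S = exp(−(a + b)t)
- F = a/(a + b) × (1 − S)

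The only rates in the documents come from the metastasis series of 20 patients and 35 tumors summarised in Protocol 3.2. Local recurrence in its 9–12 month period was 35% of patients and 20% of tumors, and 1-year survival was 89.4%, that is 10.6% deaths. These are background figures, not design inputs, so I also varied recurrence over 10–35% and recurrence-free death over 5–30% per year.

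With the series' per-patient rates, a = −ln 0.65 = 0.431 and b = −ln 0.894 = 0.112. At 5 years:

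- K = exp(−2.154) = 11.6%
- S = exp(−2.714) = 6.6%
- F = (0.431/0.543) × (1 − 0.066) = 74.1%, against 1 − K = 88.4%

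Selected 5-year results in percent (gaps computed before rounding):

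| Recurrence/yr | Death/yr | K | S | Gap | 1 − K | F | Gap |
|---|---|---|---|---|---|---|---|
| 10 | 5 | 59.0 | 45.7 | 13.4 | 41.0 | 36.5 | 4.4 |
| 10 | 30 | 59.0 | 9.9 | 49.1 | 41.0 | 20.5 | 20.4 |
| 20 | 10.6 | 32.8 | 18.7 | 14.1 | 67.2 | 54.1 | 13.1 |
| 35 | 5 | 11.6 | 9.0 | 2.6 | 88.4 | 81.3 | 7.1 |
| 35 | 10.6 | 11.6 | 6.6 | 5.0 | 88.4 | 74.1 | 14.3 |
| 35 | 30 | 11.6 | 2.0 | 9.7 | 88.4 | 53.6 | 34.8 |

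Over the whole grid the 5-year overstatement is 2.6 to 49.1 points for recurrence-free survival and 4.4 to 34.8 points for recurrence risk. At 1 year it is 3.3 to 27.0 and 0.2 to 5.2 points.

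**Finite samples.** In 5,000 simulated trials at each of n = 30 and n = 40, with 20% recurrence and 10.6% death per year, mean K at 5 years was 32.7% and 32.8%, against mean S of 18.6% and 18.7%. Mean 1 − K was 67.3% and 67.2%, against mean F of 54.2% and 54.1%. Both inequalities held in every trial.

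**The case against.** The strongest reply is that the SAP governs the analysis and its name fits its event. The event and the censoring of deaths are explicit in both documents. A death-censored Kaplan-Meier curve is a recognised description of time to recurrence, if censoring by death is non-informative. On that view the misnomer is one sentence in the protocol, and preferring cumulative incidence is a choice of estimand.

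Much of this stands. The naming error is confined to Protocol 11.5.4, and the SAP should not be called mislabelled. Two things do not fall away. The protocol's sentence is still uncorrected. And neither document states the non-informative censoring assumption, which is doubtful when progression can precede death between yearly scans.

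A reader might infer three stronger points that the documents do not support:

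- That the plan reports one minus the curve as the risk of recurrence. Neither document says so. It is a misreading that the plan leaves open.
- That this curve will be used to size the pivotal study. Protocol 11.2 and SAP Sample Size Justification say in general that study estimates will be used for power. They do not name this curve, and the efficacy endpoint is local tumor control by visit.
- That deaths are concealed. Overall survival counts every death, and SAP Subject Disposition tabulates them.

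**Conclusion.** The label in Protocol 11.5.4 is wrong as written. The SAP's name is right, but its curve cannot be turned into a recurrence probability by subtraction. The direction of both overstatements is certain and needs no assumption about rates. They vanish only if no death without recurrence intervenes, which is implausible in this population over 60 months.

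The size cannot be fixed from the documents. The range of about 3 to 49 points for recurrence-free survival and 4 to 35 points for recurrence risk at 5 years rests on constant hazards and assumed rates. With the cited series' rates, the 60-month comparisons are 11.6% against 6.6% and 88.4% against 74.1%. That case extends about a year of local recurrence over five years and treats every death as recurrence-free. The latter is an upper-end assumption, because a death after a counted recurrence causes no bias.

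The importance is moderate. This is a supportive endpoint in a descriptive study that is not powered for formal analysis, and no error rate or sample size changes.

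**What to change.** 1. Use one name for the measure in Protocol 5.3, Protocol 11.5.4 and the SAP section Disease recurrence or progression. Stop calling the death-censored curve recurrence-free survival.
2. In the SAP, report the cumulative incidence of recurrence or progression with death as a competing event, using the Aalen-Johansen estimator.
3. If recurrence-free survival is reported, define its event as whichever comes first of recurrence, progression or death from any cause.

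The cost is wording in both documents and one extra estimator. The dates of recurrence and death are already needed for the planned curves. Item 3 gives a less favourable figure than the present curve. Item 2 gives a recurrence risk lower than one minus that curve.
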